## 12.5. Causality Assessment

An AE is not automatically related to the study device or procedure simply because the subject is wearing the device and participating in the study. The event should be reviewed to determine if the device or study procedure could have possibly caused the event and therefore is related to the study device or procedure. It should also be noted that should the control arm utilize a non-medtronic device (such as a insulin pen) these would not be considered device related.

Causality assessment is the determination of the relationship between an AE and the device being studied. It is expected that the investigational center will review all elements surrounding the AE to properly assess the causality of the event to the study device or to a study procedure.

This review would include the subjects' description of the event, study device uploads and medical records (if applicable) from the treating facility. These records will be made available to sponsor.

Investigators should classify the relationship between the AE and the study device or study procedures using one of the five possible causality categories listed below:

- a) **Not related:** relationship to the device or procedures can be excluded when:
  - o the event is not a known side effect of the product category the device belongs to or of similar devices and procedures
  - o the event has no temporal relationship with the use of the investigational device or the procedures;
  - o the event does not follow a known response pattern to the medical device (if the response pattern is previously known) and is biologically implausible;
  - o the discontinuation of medical device application or the reduction of the level of activation/exposure - when clinically feasible – and reintroduction of its use (or increase of the level of activation/exposure), do not impact on the serious event;
  - o the event involves a body-site or an organ not expected to be affected by the device or procedure;
  - o the event can be attributed to another cause (e.g. an underlying or concurrent illness/ clinical condition, an effect of another device, drug, treatment or other risk factors);
  - o the event does not depend on a false result given by the investigational device used for diagnosis, when applicable;
  - o harms to the subject are not clearly due to use error;
  - o In order to establish the non-relatedness, not all the criteria listed above might be met at the same time, depending on the type of device/procedures and the serious event.
- b) **Unlikely:** the relationship with the use of the device seems not relevant and/or the event can be reasonably explained by another cause, but a relationship to the device cannot be completely ruled out.

- c) **Possible:** the relationship with the use of the investigational device is weak. Alternative causes are also possible (e.g. an underlying or concurrent illness/ clinical condition or/and an effect of another device, drug or treatment). Cases where relatedness cannot be assessed should also be classified as possible.
- d) **Probable:** the relationship with the use of the investigational device seems relevant and/or the event cannot reasonably be explained by another cause.
- e) **Causal relationship:** the event is associated with the investigational device or with procedures beyond reasonable doubt when:
  - o the event is a known side effect of the product category the device belongs to or of similar devices and procedures;
  - o the event has a temporal relationship with investigational device use/application or procedures;
  - o the event involves a body-site or organ that
    - the investigational device or procedures are applied to;
    - the investigational device or procedures have an effect on;
  - o the event follows a known response pattern to the medical device (if the response pattern is previously known);
  - o the discontinuation of medical device application (or reduction of the level of activation/exposure) and reintroduction of its use (or increase of the level of activation/exposure), impact on the event (when clinically feasible);
  - o other possible causes (e.g. an underlying or concurrent illness/ clinical condition or/and an effect of another device, drug or treatment) have been adequately ruled out;
  - o harm to the subject is due to error in use;
  - o the event depends on a false result given by the investigational device used for diagnosis, when applicable;
  - o In order to establish the relatedness, not all the criteria listed above might be met at the same time, depending on the type of device/procedures and the serious event.

**Example: A severe hyperglycemia AE with the following event description would have the following causality assessment for device relatedness:**

Improved glucose without an infusion set/site change	Not related
Changed infusion set with glucose improvement	Possible
Infusion set fell out, bent cannula, occlusion alarm	Causal relationship

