## 2. Synopsis

Title	Performance Evaluation of an Advanced Algorithm with CGM in Adults, Adolescents, and Pediatrics
Clinical Study Type	Pivotal study
Sponsor	Medtronic MiniMed, Inc. ("Medtronic") [name] [contact]
Indication Under Investigation	Type 1 diabetes, Type 2 diabetes
Devices	
Investigational Devices:
 

▪ GST3C/4C Dock

▪ GST Download Utility Software

 
Non-Investigational Devices:

	

▪ Guardian™ Connect Transmitter*

▪ Guardian™ Sensor (3)**

▪ Tester

▪ Charger

▪ One-press Serter

▪ USB cable and wall-powered adaptor for GST3C/4C Charger Dock

▪ Medtronic CareLink™ Personal Therapy Management Software for Diabetes For Clinical Research –referred to as CareLink™ Personal For Clinical Research in this protocol

▪ Ascensia CONTOUR®NEXT LINK 2.4 Blood Glucose Meter –referred to as the CONTOUR®NEXT LINK 2.4 study meter in this protocol

▪ Abbott™*/Medisense™*Precision Xtra™* meter to be used for Ketone measurements only - referred to as the Precision Xtra™* ketone meter in this protocol

▪ Oval Tape

▪ Hypafix™* Tape 4 in x10 yd

▪ Tegaderm™* 4" x 4 1/2" Dressing

 
*Commercially available device used outside their approved intended use in subjects 14 years or younger.
 
**Commercially available device used outside their approved intended use in subjects 2-6 years.

Purpose	The purpose of this study is to demonstrate the performance of the Guardian™ Sensor (3) with an advanced algorithm in subjects age 2 – 80 years, for the span of 170 hours (7 days).
Objective(s)	The primary objective of the study is to demonstrate the accuracy of Guardian™ Sensor (3) when used over a period of 7 days (i.e., 170 hours) with the system in subjects 2-80 years of age.

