## **Hypoglycemic and Hyperglycemic Challenges**

During the YSI™\* FST, subjects with a known insulin sensitivity ratio and insulin carbohydrate ratio will be randomly assigned to undergo hypoglycemic and hyperglycemic challenges (see Hypoglycemic and Hyperglycemic Challenge Guidelines).

Subjects will continue with their current diabetes regimen independent of the study devices. Subjects will be instructed by the investigational center that they are not to use the study devices (except for the study meter) for the management of their diabetes.

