# CIP324 Clinical Investigation Plan

10838519DOC

Version H

Page 74 of 173

Medtronic

(3)s at the appropriate time and sensor location. Once the study period Guardian™ Sensor (3)s are inserted, the subject should follow the YSI™\* FST SMBG requirements (Section 8.2.2.3.1).

In addition, subjects should be reminded to bring medication, syringes, insulin, and infusion sets that might be needed for their personal pumps during the YSI™\* FST visit.

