## **12.2. Reporting of Adverse Events**

The Investigator or designee will record ALL AEs while the subject is enrolled in the clinical study. Each AE needs to be assessed for its device or procedure relatedness. A device related AE is associated with the use of the study device (e.g. infection of sensor site or infusion set occlusion resulting in DKA). A procedure related AE is associated with testing related to the study procedures specified in the CIP (e.g. IV insertion pain, FST exercise injuries). This includes study procedures such as FST and lab draws.

Examples of device or procedure related AEs include:

- **Device related (ADE):** insertion site infection
- **Serious adverse device effect (SADE):** cellulitis at device insertion site requiring hospitalization
- **Procedure related AE:** bruising at IV insertion site

Subjects participating in the study have diabetes and are expected to experience hypoglycemia and or hyperglycemia. These normal events are not expected to be reported to sponsor on an AE eCRF as this is not considered an untoward event, but rather an expected occurrence. Any glycemic excursion that meets the protocol definition of Severe Hypoglycemia, Severe Hyperglycemia, or DKA is considered an untoward event and a worsening from the subject's baseline and would be reported to sponsor on an AE eCRF.

Baseline medical conditions should only be reported to sponsor on an AE eCRF if there is a worsening from the subject's baseline. For example, a subject previously diagnosed with Asthma is hospitalized for severe asthma attack would be a reportable event.

Adverse events will be documented in the subject source file and reported to sponsor on an eCRF. The investigational center is responsible for documentation of AEs including obtaining source documents related to the event, such as emergency medical technician/paramedic reports, hospital records (admission summary; lab results, test results, discharge summary) or device uploads to support the event. Source documents will be reviewed to determine if additional AEs have occurred and require reporting.

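### The device-relatedness examples in Sections 12.2 and 12.5 treat failure of the subject's own infusion set as study-device related, against the device list and the protocol's own causality criteria

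*Protocol*

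**What the plan says.** **Examples.** Protocol Section 12.2 explains a device-related adverse event as one tied to use of the study device and illustrates it with "infection of sensor site or infusion set occlusion resulting in DKA". Section 12.5 closes with a three-row example introduced by "A severe hyperglycemia AE with the following event description would have the following causality assessment for device relatedness". Glucose that improves without a set change is *Not related*. The row "Changed infusion set with glucose improvement" is *Possible*. The row "Infusion set fell out, bent cannula, occlusion alarm" is *Causal relationship*.

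**Criteria.** Earlier in Section 12.5, an event is not to be called related merely because the subject wears the device. Attribution to another cause, expressly including another device, supports *Not related*. The criteria for *Causal relationship* include that other possible causes, again including another device, have been adequately excluded. For both categories the text adds that not every criterion need be met.

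**Insulin delivery.** Section 8.1 states "Subjects will continue with their current diabetes regimen independent of the study devices". Section 8.2.2.5 has sites remind subjects to bring "infusion sets that might be needed for their personal pumps".

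**Control arm.** Section 12.5 also says that "should the control arm utilize a non-medtronic device (such as a insulin pen) these would not be considered device related". Section 5 describes a single-sample design without controls.

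**The concern.** Relatedness is meant to describe the devices under study. If the examples steer sites to code an infusion-set failure as device related, the safety record attributes to a sensor, recorder and accessories an event that arose in the subject's background therapy. The event would then carry an adverse device effect label, or a serious one, and go to the sponsor's anticipated/unanticipated assessment under Section 12.6. A worked example is what a coordinator is likely to use when coding, so it matters more than its place at the end of the section suggests. The control-arm sentence is further text that does not belong to this design.

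**Working it through.** No calculation applies. The check is whether the examples, the device list and the criteria agree.

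**1. Does any study device deliver insulin?** Section 6.1 describes 2 investigational devices, the dock and the "GST Download Utility Software". Section 6.2 has 11 entries: sensor, transmitter, tester, charger, serter, cable and adaptor, CareLink, glucose meter, ketone meter, oval tape, and other tapes, dressings or wipes. That makes 2 + 11 = 13 entries, of which 0 are a pump, infusion set, pen or syringe. Table 1 (device accountability) tracks four items: sensor, transmitter, dock and glucose meter. CareLink can accept pump uploads, but Section 6.2.7 confines it here to the study meter.

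**2. Whose infusion sets are they?** Outside Section 12 they appear as supplies subjects bring for their own pumps (Sections 8.2.2.5, 8.2.2.6.3, 8.2.2.7, 9.2.2.5, 9.2.2.6.2, 9.2.2.7) and in ketone management (Section 10.5.4).

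**3. Does the definition of device bring them in?** Section 12.1 takes in any device used in the study, including a marketed component of the system. A personal pump is neither listed nor accounted for as either. Section 12.5 ties causality to the device being studied.

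**4. Example against criteria.**

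| Event in the 12.5 example | Code given | Where the 12.5 criteria point |
|---|---|---|
| Improvement without a set change | *Not related* | No conflict |
| Set changed, glucose improved | *Possible* | Evidence implicates another device, so toward *Not related*; *Possible* only if the cause cannot be assessed |
| Set fell out, bent cannula or occlusion alarm | *Causal relationship* | Cause identified in another device, so *Not related*; other causes have not been excluded |

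The example runs in the wrong direction. The stronger the evidence that the infusion set was the cause, the higher the study-device rating, whereas under the criteria it should fall.

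**5. Could the situation arise?** Yes. Section 12.1 counts glucose above 300 mg/dL with blood ketones above 1.5 mmol/L as severe hyperglycemia. For ketones above 1.5 and below 3 mmol/L, Section 10.5.4 has pump users change the catheter and receive correction insulin. If glucose then improves, the second row yields *Possible*, whether or not the set had failed. Sections 8.2.2.6.3 and 9.2.2.6.2 also anticipate occlusions, since subjects are asked to bring spare sets.

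**6. How many events?** Not estimable. The documents give neither the share of subjects on pumps nor an expected rate of infusion-set failure.

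**The case against.** The best defence is that the examples only illustrate. The operative criteria sit above them and point the right way. In addition, Section 13.1 sets up a CEC of external physicians experienced with insulin pumps and CGM, who may review severe hyperglycemia and DKA and can disagree with the investigator. Both points limit the harm, but neither removes the contradiction. The CEC has no instruction on infusion-set events, and its three categories are the same three used in the example.

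Several stronger readings are tempting, and the documents do not support them:

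- *Every infusion-set event will be misclassified.* This assumes that all sites follow the example over the criteria and that no CEC review corrects them.
- *The reported device-related rate will be wrong.* Neither document specifies such a rate. Protocol Section 15.13 and SAP Section 7.9.12 plan a descriptive summary of skin assessments and all adverse events.
- *Study devices cannot cause hyperglycemia.* Section 11.1 lists hyperglycemia as a possible result of improper insertion with the serter, and subjects may use the study meter to manage their diabetes.
- *Pump users are treated differently from pen users by rule.* The pen exemption is confined to a control arm that does not exist, so it has no effect here.
- *These are the most likely serious events, over 460 subjects for 90 days each.* No source ranks the events. The 460 is an enrollment ceiling counted from consent, so it includes screen failures; 244 are to complete. Ninety days is the maximum participation, including replacements and repeats. Some adults do not require insulin at all.
- *False unanticipated-effect reports will follow.* An event named in the protocol counts as anticipated under Section 12.6. DKA is a listed challenge risk in Section 11.1, and Section 12.2 itself names infusion set occlusion leading to DKA.

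**Conclusion.** The point stands as an internal contradiction in safety coding. Sections 12.2 and 12.5 contain examples that label failure of the subject's own infusion set as study-device related, while the device list contains no insulin-delivery device and the criteria in Section 12.5 point to *Not related*. A site that follows the examples would record the wrong relatedness code, and severe hyperglycemia or DKA traced to an infusion set would become an adverse device effect.

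The impact is confined to relatedness coding and the Section 12.6 assessment. Its size cannot be given in events. The safety analysis is descriptive, and the accuracy endpoints, alpha and sample size do not depend on it. The conclusion assumes that the Section 6 list is complete for this study and that personal pumps are not a component of the studied system; nothing in the documents says otherwise.

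**What to change.** Reconcile Sections 12.2 and 12.5 with the Section 6 device list:

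1. Delete the infusion-set example from Section 12.2 and keep the sensor-site infection.
2. Replace the worked example in Section 12.5 with events from listed devices, such as sensor-site infection, adhesive reaction or sensor fracture.
3. State that a failure of the subject's own insulin-delivery equipment is not in itself a study-device failure and is assessed under the existing criterion for another device. A blanket *Not related* rule would go too far. Procedure relatedness, and any contribution from a listed device such as the study meter, should stay open to case review.
4. Delete the control-arm sentence.
5. Give the CEC the same wording.

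The cost is protocol text and matching guidance for sites and the CEC. All adverse events are still collected, and only the relatedness code is affected. Any infusion-set events already coded under the example should be looked at again.

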## **12.6. Anticipated or Unanticipated**

If an AE is determined to be related to the study device, the sponsor will then assess the event to determine if it is anticipated or unanticipated.

- **Anticipated:** the event is identified in the CIP; labeling; report of priors/Investigator's Brochure (IB) or user guide.
- **Unanticipated:** the event has not been previously identified in the CIP; labeling; report of priors/IB, or user guide.

## **12.7. Skin Assessment: Glucose Sensor Insertion Sites**

Skin irritation may be associated with the insertion of the device or device wear and may be associated with the adhesives and tapes used to secure the study devices. The area of skin associated with device insertion and wear will be assessed following the removal of each device by investigational center staff. Either subject or investigational center may remove a device if they are concerned with skin irritation or skin discomfort. The Investigational Center staff will complete a skin assessment each time a study device is removed from a subject, independent of the length of time inserted or the amount of time elapsed between device removal and the assessment.

It is expected that subjects will experience mild irritation, redness, bleeding or bruising associated with the insertion and or wear of the glucose sensor and devices. These events are to be documented and captured on the Skin Assessment eCRF. An AE eCRF will only be completed if the skin assessment observation meets the following criteria:

- Infection
- Any observation that meets the criteria of moderate or severe per the skin assessment case report form (for example: bruising equal to or greater than 6 cm in longest diameter; rash that requires prescription medication)

Subjects will not be required to return to the investigational center for examination to document resolution of Skin Assessment observations. The subject should be instructed to contact the investigational center for follow-up if there is any worsening or change that concerns the subject. Worsening should be assessed to determine if AE reporting is necessary.

## **12.8. Documentation of Symptoms During Frequent Sample Testing**

During FST it is expected that subjects may experience minor symptoms that are related to the procedure requirement of driving glucose levels high and low. All symptoms experienced by the subject must be recorded on the appropriate log. Those symptoms that are minor and directly associated with the requirements of the FST would be recorded on the log only. Examples include:

- leg cramp or muscle discomfort related to exercise
- headache
- shakiness/tremors
- discomfort associated with IV insertion
- shortness of breath

Events that are more serious should be noted on the log and reported as AEs. This would include:

- Severe Hypoglycemia
- Diabetic ketoacidosis
- Seizure
- Vomiting
- Chest pain
- Syncope/Fainting
- Shortness of breath unrelated to physical activity

## 13. Data Review Committees

### 13.1. Clinical Events Committee

A clinical events committee (CEC) consisting of external physicians with an expertise in endocrinology and the management of diabetes including insulin pumps and CGM will be convened. The CEC will review all AEs as required per protocol, and may include reports of:

- Serious Adverse Event
- Serious Adverse Device Effect
- Unanticipated Adverse Device Effect
- Severe Hypoglycemia
- Diabetic Ketoacidosis
- Severe Hyperglycemia

The CEC will review the following events within 7 days from the time the sponsor is notified.

- DKA during Hypoglycemic and Hyperglycemic Challenges
- Severe hypoglycemia with seizures or requiring glucagon during Challenges

CEC will act as DMC in this situation and will provide recommendation to the sponsor on the following:

- a) If enrollment and study may continue
- b) If enrollment should be stopped; enrolled subjects are still allowed to continue in study
- c) If the entire study must be stopped, including subjects who have already received study devices.

The CEC will assess events to determine agreement or disagreement with the investigator classification of an event. The CEC will only provide three causality assessments for device and procedure relatedness: Not Related, Possible, and Causal relationship.

Causality Categories for Investigational Center		Causality Categories for CEC:

• Not Related

• Unlikely

• Possible

• Probable

• Causal relationship

		

• Not Related

• Possible

• Causal relationship

The sponsor will notify the investigator of any disagreement in assessment of an event by the CEC.

## 14. Device Deficiencies and Troubleshooting

The Medtronic 24-Hour TS will be consulted for device troubleshooting (e.g. assistance is needed by subject to operate their device(s)). When subjects call the TS, they are instructed to notify the TS operator that they are currently participating in a clinical research study. All device deficiencies that are reported to the TS will be documented by the TS staff.

The investigational center will be provided with a copy of all TS calls for their subjects. The TS calls should be reviewed for investigational center staff awareness for the possibility of an AE. If an AE is detected the investigational center staff will complete the appropriate eCRF(s).

All device deficiencies reported directly to the investigational center staff by a subject should either be reported to the TS by the subject or investigational center staff. Any device deficiency the investigational center may have should be reported to the TS. A device deficiency is any inadequacy of a medical device with respect to its identity, quality, durability, reliability, safety, or performance. NOTE: Device deficiencies include malfunctions, use errors, and inadequate labeling. (**Adapted from ISO14155:2011**)

